Patients with neuropsychological diagnoses are reported to be more likely to develop severe COVID-19 disease. Previous work has shown an increased incidence of severe respiratory infection and worse critical care outcomes associated with pharmacological neuropsychological treatments. It remains unclear whether particular conditions or treatments predispose to severe COVID-19 disease (requiring hospital, critical care admission or death) more than to other acute respiratory infections. Patients with COVID-19 disease are reported to subsequently have a high incidence of neuropsychological disease. However, the incidence of neuropsychological sequelae is also high following other critical illness. It is unclear whether neuropsychological sequelae following severe COVID-19 disease are more serious or managed differently than following other severe acute respiratory infection (SARI) such as bacterial or viral pneumonia, particularly when accounting for risk factors associated with the disease.

Antecedent analysis

We will explore the associations between pharmacological treatments (hypnotics and anxiolytic, antidepressant, drugs used in psychoses and related disorders) of preexisting neuropsychological diagnoses (anxiety, mood, psychotic disorders, or dementia), and severe clinical outcomes of COVID-19 infection (hospital admission, ICU admission and death) in comparison to those not receiving such treatments.

We will determine whether the associations between pre-existing neuropsychological treatments and severe clinical outcomes differ for patients with COVID-19 infection in comparison to patients with non-COVID-19 severe acute respiratory infections (SARI)

Sequelae analysis

We will determine the risks of receiving a new neuropsychological diagnosis or new neuropsychological medication within one year after discharge from hospital for patients admitted with COVID-19 infection in comparison to patients with non-COVID-19 severe acute respiratory infections (SARI) investigating the subgroups of hospitalised patients admitted to and not admitted to an ICU.

INTRODUCTION

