This study will investigate neuropsychological disease and treatments before and after severe COVID-19 disease. The two main aims are:

1. to evaluate the associations of pre-existing neuropsychological diseases and treatments with severe COVID-19 outcomes in comparison to patients without pre-existing neuropsychological pathology;

2. to evaluate the associations between hospital or ICU admission due to COVID-19 and neuropsychological sequelae following discharge home in comparison to patients with ICU admission due to non-COVID-19 severe acute respiratory infections (SARI).

Objectives

- 1. To assess whether pre-existing neuropsychological diseases (by separate diseases and overall) are associated with severe COVID-19 outcomes (hospital and ICU admission and death) in comparison to the general population.
- 2. To assess whether pre-existing neuropsychological treatments (as a class and individually where possible) are associated with severe COVID-19 outcomes (hospital and ICU admission and death) and whether these explain disease associations in comparison to those not receiving such treatments.
- 3. To assess whether the risk of severe COVID-19 outcomes with prior neuropsychological disease differs from the risk of severe outcomes with SARI.

After discharge following a hospital admission for COVID -19 infection:

- 4. To assess the incidence of new neuropsychological diseases up to one year after hospital and ICU discharge following treatment for COVID-19 disease.
- 5. To compare the incidence of new neuropsychological diseases up to one year after hospital and ICU discharge with COVID-19 disease to the incidence following discharge after treatment for SARI.

Summary of the potential impact

This study will provide a better understanding of how pre-existing psychopathology and concomitant medication affect the risk of hospital and ICU admission and death due to COVID-19 and how any differences between those with and without preexisting psychopathology and COVID-19 infection compare to other severe acute respiratory infections. We will discover the neuropsychological sequelae of admission to a hospital or ICU with COVID -19 disease, taking into account prior neuropsychological disease and whether these differ from patients discharged from an ICU following SARI. These findings will be key to prevention and management of ongoing problems for these patients.

METHODS

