The following variables of interest were chosen as either due to known association with risk of developing severe COVID-19 and/or known associations with neuropsychological disease. Distributions of each variable will be summarised by cohort using descriptive statistics.

Demographics (Aims 1 & 2)

- Age
- Gender
- Material deprivation by quintile of Townsend deprivation score

- Ethnicity (White, Indian, Pakistani, Bangladeshi, other Asian, Black African, Chinese, and other ethnic group),
- Geographical region
- Domicile (homeless, care home residence, neither)
- Household size

Lifestyle (Aims 1 & 2)

- Body mass index (BMI)
- Smoking status (non-smoker, ex-smoker, light smoker: 1–9 cigarettes/day, moderate smoker: 10–19 cigarettes/day, heavy smoker: ≥20 cigarettes/day, not recorded)
- Alcohol intake (none, trivial: <1 unit/day, light: 1–2 units/day, medium: 3–6 units/day, heavy: 7–9 units/day, very heavy: >9 units/day, not recorded).

Co-morbidities (Aims 1 & 2)

- Cardiovascular diseases coronary heart disease, stroke/transient ischaemic attack, atrial fibrillation, congestive cardiac failure, thromboembolism, peripheral vascular disease, congenital heart disease, hypertension
- Respiratory diseases asthma, chronic obstructive pulmonary disease, rare lung conditions (bronchiectasis, cystic fibrosis, alveolitis), pulmonary hypertension or pulmonary fibrosis
- Endocrine diseases type 1 and 2 diabetes, hypothyroidism
- Chronic kidney disease
- Neurological conditions- epilepsy/seizures, Parkinson's disease, motor neurone disease, multiple sclerosis, myasthenia gravis, Huntington's disease
- Cancer blood cancer, respiratory tract cancer, and other relevant cancer
- Bone and joint conditions- osteoarthritis, rheumatoid arthritis or Systemic Lupus Erythematosis (SLE), osteoporosis, osteoporotic fracture (hip, spine wrist, humerus)
- Gastrointestinal diseases liver disease, liver cirrhosis
- Transplants solid organ transplant (excluding kidney and bone marrow), bone marrow or stem cell transplant
- Sickle cell disease or severe immunodeficiency
- Traumatic brain injury
- Learning disability/Down's syndrome, cerebral palsy

Medications/treatments (Aims 1 & 2)

- antihypertensive drugs,
- aspirin,
- statins,
- Anticoagulants,
- non-steroidal anti-inflammatory drugs,
- bisphosphonates,
- oral contraceptives,
- hormone replacement therapy,

- anticonvulsants
- chemotherapy
- radiotherapy
- immunosuppressant medication
- leukotriene or long-acting beta-agonist

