- oral steroids

Intensive care stay (Aim 2)

- Length of stay
- Duration of advanced respiratory support (invasive ventilation)
- Use of sedation in the first 24 hours of admission

Effect Modifiers

For aim 1, we assessed these potential confounders by creating directed acyclic graphs (DAG) to determine which variables were likely to be to some extent caused by the presence of prior neuropsychological disorders (as the exposure of interest), and which were not likely to be caused by the presence of prior neuropsychological disorders, but were thought to be independently potential predictors of severe Covid outcomes.

Variables from the above list to be included in the model are all those grouped under: demographics; co-morbidities; lifestyle factors; plus prescription of any immunosuppressants and/or anticoagulants. Other medications (as these are not believed to affect the risk of severe Covid outcomes), and in-hospital factors (length of stay and use of sedation during intensive care admission, as these are outcomes potentially caused by Covid severity) will not be adjusted for.

For aim 2, our exposure of interest is admission to intensive care with SARI (compared to admission to intensive care with SARI. This exposure occurs at a fixed time which is used as the baseline for our time to event analysis in predicting the outcome of interest, and all other variables listed above are measured before this baseline. Therefore (depending on the available sample size and number of events), all the previously listed covariates of interest may be included in our adjusted models.

Data sources

Intensive Care Unit admission data will come from the ICNARC CMP dataset Hospital admission and mortality will come from the HES dataset

All exposures and confounders and neuropsychological outcomes will come from the QResearch database.

COVID-19 infection test status will come from the national registry of COVID-19 RT-PCR positive test results from Public Health England (PHE).

Bias

To limit the possible impact of COVID-19 testing bias (collider bias) we will analyse the entire QResearch eligible population, rather than restricting analysis to only those with a positive COVID-19 test.

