Royston Parmar flexible parametric survival models will be used to estimate the hazard ratio of severe COVID-19 outcome (hospital or critical care admission and death) in cohort 1 for patients with neuropsychological disease at study entry compared with those without disease, and for individual neuropsychological diseases and treatments.

This analysis will be adjusted for the listed covariates. The age variable will be included as a restricted cubic spline rather than a linear term. Before commencing analysis, we will assess the numbers of patients with each comorbidity, and may if necessary group the presence of certain less common comorbidities together. Any such grouping will be done on the basis of clinical similarities only and prior to examining any outcomes by comorbidity. We may also include a time-varying binary covariate to record any new diagnosis and/or treatment which occurs after study entry in patients originally free from both diagnosis and treatment, depending on the number of these events. Proportional hazards assumptions will be tested, and time dependent terms will be included if the hazard ratio changes over time (I.e. if the association between neuropsychological disease and risk of severe COVID-19 has changed during the course of the pandemic). A random frailty term will be included to account for similarities amongst patients registered in the same primary care practice. Possible interactions between exposure and age, sex and ethnicity will be considered and tested using a Wald test.

The same methods will be used for secondary analyses in which the main exposure variable will be defined as either the presence of a specific class of neuropsychological disorder or any other neuropsychological disorders or no disorder.

The primary analysis will be used to estimate the hazard ratio of severe SARI outcomes in cohort 2 using the same exposure variables.

If non-proportional hazards are observed in either cohorts 1 or 2, then maximum follow-up time will be capped at 1 year and a time-dependent covariate will be added to the analysis of both cohorts to maintain the comparability of results.

Aim 2.

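### The Aim 1 analysis by class of disorder, on its plain reading, gives total associations and does not isolate the effect of a specific condition

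*Protocol*

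**What the plan says.** Objective 1 of the protocol is "To assess whether pre-existing neuropsychological diseases (by separate diseases and overall) are associated with severe COVID-19 outcomes". Under Statistical Methods, Aim 1, the disease-specific part is left to secondary analyses that reuse the primary model with a different main exposure. For each class in turn, that exposure is coded as "either the presence of a specific class of neuropsychological disorder or any other neuropsychological disorders or no disorder".

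For the primary analysis, whose covariates therefore carry over, the protocol says "This analysis will be adjusted for the listed covariates". The Effect Modifiers section limits these for Aim 1 to "all those grouped under: demographics; co-morbidities; lifestyle factors; plus prescription of any immunosuppressants and/or anticoagulants". The co-morbidity list under Covariates includes neurological conditions ("epilepsy/seizures, Parkinson's disease, motor neurone disease, multiple sclerosis, myasthenia gravis, Huntington's disease"), traumatic brain injury and learning disability. It does not include anxiety, mood disorder, psychotic disorder or dementia.

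Definition of exposures (Aim 1) counts a diagnosis recorded at any time in the past. Nothing makes the four classes mutually exclusive. The Bias section expects some conditions to protect and others to do the reverse, and says the secondary analysis was added to look at specific conditions for that reason. Cohort 2 is to be analysed with the same exposure variables.

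**The concern.** Membership of the first exposure level depends only on having the class in question. The second level is then naturally the patients who have some disorder but not that one. Someone with both anxiety and dementia is in the first level of the anxiety model and in the first level of the dementia model, and neither model adjusts for the other diagnosis.

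The reference level excludes everyone with any of the four classes. The exposed group therefore contains people with other classes while the reference group contains none, so the contrast picks up the other classes even when disorders co-occur only by chance. If conditions act in opposite directions, as the Bias section expects, this coding can create, blur or hide the very contrast it is meant to show. No listed sensitivity analysis separates the classes. In a cohort of about 8.3 million adults a small carried-over association can also come with a narrow interval and be read as a finding about that condition.

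The point concerns the hazard ratios for classes of disease, not those for classes of drug.

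**Working it through.** **No figure to reproduce.** The protocol gives no effect size, prevalence, overlap or event count for this analysis. What follows combines a reading of the text with an illustration on assumed inputs.

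**Step 1: coding against adjustment set.** Exposure: the class present, another disorder, or none (Statistical Methods, Aim 1). Covariates: demographics, co-morbidities, lifestyle, immunosuppressants and anticoagulants (Effect Modifiers, Covariates). None of the four classes appears among the covariates. The absence of mutual adjustment is therefore firm. The placement of patients with several classes is the plain reading, not an explicit statement.

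**Step 2: what the contrast estimates.** Take a rare outcome, multiplicative hazards and no other covariates. Let q be the share of class-X patients who also have class Y. Then

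HR(X versus no disorder) = HR_X × [(1 − q) + q × HR_Y].

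For a class with no effect of its own (HR_X = 1):

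| Assumed HR_Y | q = 10% | q = 30% | q = 50% |
|---|---|---|---|
| 1.5 | 1.05 | 1.15 | 1.25 |
| 2.0 | 1.10 | 1.30 | 1.50 |
| 3.0 | 1.20 | 1.60 | 2.00 |

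- Low end: q = 6% and HR_Y = 1.5 give 0.94 + 0.06 × 1.5 = 1.03.
- Chance overlap only: if Y is dementia at an assumed 6% prevalence in older patients with HR 3, and is independent of X, the result is 0.94 + 0.06 × 3 = 1.12.
- Protective co-occurring class: q = 30% and HR_Y = 0.8 give 0.70 + 0.30 × 0.8 = 0.94.
- The distortion vanishes if q = 0 or HR_Y = 1.

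**Step 3: four correlated classes.** This is a simulation of 2,000,000 patients with assumed prevalences of 15% (anxiety), 17% (mood), 1.2% (psychotic) and 1.2% (dementia). The shares with at least one other class came out at 48%, 43%, 75% and 49%.

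| Class | True HR | Three-level contrast | All four indicators together | Class X only versus none |
|---|---|---|---|---|
| Anxiety | 1.0 | 1.20 | 1.00 | 1.00 |
| Mood | 1.2 | 1.30 | 1.19 | 1.18 |
| Psychotic | 2.0 | 2.40 | 2.02 | 2.07 |
| Dementia | 3.0 | 3.43 | 3.12 | 3.14 |

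The 3.12 for dementia is compatible with sampling error. About 2,000,000 × 0.012 = 24,000 patients at a risk near 0.01 × 3 × 1.4 = 4.2% give about 1,000 events, so the standard error of the log hazard ratio is about 1/√1,000 = 0.03, against ln(3.12/3.0) = 0.04. The joint model recovers the inputs because the data were generated from a multiplicative model of that form. This shows that the mechanism works as described, not that real data will follow it.

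**Step 4: precision.** With 8.3 million adults (Study Size), an assumed 15% with anxiety and an assumed risk of 0.8%, there are 8,300,000 × 0.15 × 0.008 = 9,960 events in that group. The 95% half-width on the log scale is then about 1.96/√9,960 = 0.02, or about ±2%, slightly more once the reference group is counted. At such precision even 1.03 would exclude 1.

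**The case against.** Five points can be made for the plan as it stands.

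- **The overlap rule is not stated.** A reader might infer that the protocol explicitly puts everyone with class X into that level whatever else they have. It does not say so. If patients with several classes were instead placed in the other-disorder level, the first level would be class X only and the carry-over would largely disappear, as the last column of the simulation shows. Nothing in the text supports that alternative, but the coding half of the point remains a reading.
- **Objective 1 asks about association.** A reader might infer that Objective 1 cannot be answered. Its wording is satisfied by a total association. The tension is with the purpose stated in the Bias section.
- **Mutual adjustment is not neutral.** With diagnoses counted whenever recorded, one class may be a consequence of another, and adjusting for it raises the issue that the protocol's own causal diagrams were drawn to address. The Aim 1 diagram is not shown, so the authors' view of how the classes relate cannot be checked. This stands, and it argues for reporting both estimates rather than replacing one by the other.
- **The size is assumed.** The illustration has no covariates. Adjustment for age, care-home residence and co-morbidities could change both overlap and class effects. This stands.
- **A statistical analysis plan could settle it.** It could settle the overlap rule. However, the protocol itself fixes both the three-level exposure and the covariate set, so the absence of mutual adjustment is a choice already made.

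**Conclusion.** The point holds in a limited form. On the plain reading, each class-specific hazard ratio is a total association, anyone with the class versus no disorder, and does not isolate the specific condition. For a class with no effect of its own, assumed overlaps of 6% to 50% with a class of hazard ratio 1.5 give roughly 1.03 to 1.25. Stronger overlap with a more harmful class gives more, and a protective co-occurring class gives less than 1. The documents fix neither the size nor the direction, so it does not follow that the ratios will be inflated.

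A reader might also infer that the three-level analysis is invalid and must be replaced, or that the main Aim 1 result is compromised. Neither is supported. The three-level contrast is legitimate when labelled for what it is, and these are secondary analyses. The primary Aim 1 contrast (neuropsychological disease versus none) and Aim 2 do not use this coding. This is a cheap and worthwhile improvement to the only planned analysis by class of disease, not a flaw that undermines the study.

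**What to change.** 1. State where a patient with more than one class is placed in the three-level exposure.
2. Keep the three-level contrast and label it as a total association.
3. Add, in cohorts 1 and 2, one model with four binary indicators (anxiety/stress, mood, psychotic, dementia) entered together, with none of the four as reference. Alternatively use the levels class X only, class X plus others, others only, and none.
4. Base statements about specific conditions on the added model, and report both sets of estimates side by side.

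The cost is a few sentences and one extra model per cohort, with data already held. The small downside is that mutually adjusted ratios are conditional on the other classes and may adjust for a class that follows from another. That is why both sets should be shown.

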A retrospective cohort data linkage study of patients aged 18 years and above registered in English general practices. This protocol is written following RECORD guidance [12].

Settings Describe the setting, locations, and relevant dates, including periods of recruitment, exposure, follow-up, and data collection.

1205 general practices in England contributing to the QResearch database, which is nationally representative. We defined cohorts during the COVID pandemic as between 24th January 2020 (the date of the first confirmed COVID-19 case in England) and study end (30th June 2021). We defined retrospective comparison cohorts as the 5 years prior to this date (24th January 2015- 23rd January 2020).

Data linkage

The study will include adult patients registered with the QResearch database. Practices must have been contributing to the QResearch database for at least 12 months. For the investigation of associations of pre-existing neuropsychological diseases and treatments (cohort 1) patients must be registered for at least a 12-month period before 24th January 2020. For the investigation of incidence of new neuropsychological diseases (cohort 2) patients must be registered for at least a 12-month period between January 2015 to 2020. The date of study entry is separately defined below for each study cohort.

Patients in QResearch will be linked to: (1) the ICNARC Case Mix Programme (CMP) database, the national clinical database from adult critical care; (2) the Hospital Episode Statistics (HES) data warehouse containing records of all patients admitted to NHS hospitals and Emergency departments in England; (3) the national registry of COVID-19 RT-PCR positive test results from Public Health England (PHE); and (4) Office of National Statistics COVID-19 mortality data, which includes all deaths due to COVID-19 in England. Data linkage will be based primarily on NHS number. For a description of the datasets see Supplemental material S1.

Participants

Give the eligibility criteria, and the sources and methods of selection of participants. Describe methods of follow-up. The methods of study population selection (such as codes or algorithms used to identify subjects) should be listed in detail.

Aim 1.

From the linked dataset, we will extract two cohorts to explore the association between neuropsychological diseases and treatments and hospitalisation, ICU admission or death:

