- Cohort four will include adult patients (aged 18+ on date of hospital admission) discharged alive following a hospital admission including an ICU admission resulting from SARI (defined below) admitted between 24 January 2015 and 23rd January 2020, who were registered in a primary care practice within the QResearch programme before their ICU admission. The cohort will allow comparisons to be made with cohort three. Follow-up will be from the date of discharge. Patients will be censored at the earliest of first occurrence of deregistration from the GP practise, death from other causes, 12 months post discharge from hospital or date of the final data extract from the linked datasets.
- Cohort 5 will include adult patients (aged 18+ on date of hospital admission) discharged alive following a hospital admission including an ICU admission resulting from SARI (defined below) between 24 January 2020 and study end date, who were registered in a primary care practice within the QResearch programme before their ICU admission. It will be used to allow comparison with cohort 3. Patients will be censored at the earliest of first occurrence of deregistration from the GP practice, death from other causes, 12

months post discharge from hospital, or date of the final data extract from the linked datasets.

Variables

Definition of outcomes Aim 1

For cohort one, our primary outcome is the first occurrence of any one of the following:

1. Hospital admission resulting from COVID-19 infection defined as testing positive for SARS-CoV-2 (as recorded in the PHE database) in the 14 days prior to or during a hospital admission period in the HES dataset, or having an ICD10 code U07.01 for confirmed COVID-19 diagnosis in that HES admission record

2. Admission to an ICU resulting from COVID-19 infection which will be defined as patients admitted to an ICU within the ICNARC dataset of COVID-19 admissions.

3.All - cause mortality following COVID-19 infection.

Secondary outcomes are each of the three events defined above, considered separately (i.e. COVID-19 hospital admissions; ICU admission; death).

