For aim 1, the various different neuropsychological conditions of patients in cohort 1 are likely to result in varying levels of exposure to covid-19, compared to the populations without these conditions, with some conditions likely to have a protective effect, but in other conditions the reverse is expected. We have added a secondary analysis to examine the effect of specific conditions in order to evaluate this.

For aim 2, the two cohorts have experienced their exposure of interest (ICU admission with either COVID or SARI) during different time frames. Patients with SARI (admitted to ICU between 2015 to 2020) will have longer follow-up, but patients with COVID (admitted to ICU during 2020/21) may have benefited from the recently increasing public awareness of mental health conditions. To combat this, we have capped all follow-up at a maximum of 1 year post ICU discharge, and we will include a time-dependent covariate to assess whether risk varies with time post discharge. We have also included a cohort of patients with SARI admitted during 2020/21 for comparison with the COVID cohort during the same time frame.

We will derive the E-value to estimate the extent unmeasured confounding.

Study Size

For aim 1 we will use the entire QResearch database of approx. 8.3 million adult patients to maximise precision and minimise selection bias. We chose to use the last 5 years of ICNARC data for SARI comparisons to use recent data whilst having sufficient numbers for comparison taking into account the numbers from previous studies and after linkage [13, 14].

For aim 2, we will use all known ICU admissions from the ICNARC database for SARI and/or COVID who can be linked to the QResearch database. In cohort 3 the expected sample size is in the region of 11,000 admissions in total, for cohort 4 it is likely to be in the region of 7,000 admissions per year, and for cohort 5 around 3,500 patients.

Quantitative variables

Quantitative variables will be treated as continuous variables without categorisation. Descriptive summary statistics (mean and standard deviation, median interquartile range or number (%) as appropriate) will be used to present sociodemographic and clinical characteristics of patients with and without COVID-19 infection for those with and without neuropsychiatric conditions or treatments.

Statistical Methods

Aim 1.

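### Objective 3 compares COVID-19 in 2020/21 with SARI in 2015-2020 only, so a difference between the two hazard ratios cannot be assigned to disease rather than period; a same-period SARI analysis in the cohort 1 population would help at low cost

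*Protocol*

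**What the plan says.** The third objective (Objectives) is "To assess whether the risk of severe COVID-19 outcomes with prior neuropsychological disease differs from the risk of severe outcomes with SARI".

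The periods are set under Settings. The pandemic cohorts are introduced with "We defined cohorts during the COVID pandemic as between 24th January 2020" and run to 30 June 2021. For the comparators the text reads: "We defined retrospective comparison cohorts as the 5 years prior to this date (24th January 2015- 23rd January 2020".

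For cohort 1, the outcome definitions for Aim 1 cover COVID-19 events only. The first component begins "Hospital admission resulting from COVID-19 infection defined as testing positive for SARS-CoV-2", and the secondary list adds nothing else: "Secondary outcomes are each of the three events defined above, considered separately (i.e. COVID-19 hospital admissions; ICU admission; death". For cohort 2 the outcome is SARI hospital admission (J09-J22), SARI intensive care admission (a list of RE codes) or death, each also taken separately.

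Under Statistical Methods, Aim 1, the whole SARI analysis is this: "The primary analysis will be used to estimate the hazard ratio of severe SARI outcomes in cohort 2 using the same exposure variables".

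The Bias section treats the two aims differently. For Aim 1 it says that "the various different neuropsychological conditions of patients in cohort 1 are likely to result in varying levels of exposure to covid-19", and it answers with analyses by specific condition. For Aim 2 it notes that the groups were admitted in different time frames and adds cohort 5: "We have also included a cohort of patients with SARI admitted during 2020/21 for comparison with the COVID cohort during the same time frame".

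**The concern.** Every COVID-19 estimate in Aim 1 comes from the pandemic period and every SARI estimate from before it. If the two hazard ratios differ, the infection may be the reason. The other possibility is that the link between neuropsychological disease and severe respiratory outcomes itself changed in 2020/21, for instance through group-specific changes in contact or in admission. The planned analyses cannot tell these apart.

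At stake is the reading of Objective 3: whether neuropsychological disease, and by the same methods its treatment, predisposes to severe COVID-19 more or less than to other severe respiratory infection. The within-cohort hazard ratios for COVID-19 (Objectives 1 and 2) are not affected.

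**Working it through.** The protocol gives no sample size, power or precision figure for Objective 3, so there is nothing to reproduce. The check has four steps.

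**1. Do the windows overlap?** Cohort 1 runs from 24 January 2020 to 30 June 2021: 524 days, and 524/365.25 = 1.43 years. Cohort 2 runs from 24 January 2015 to 23 January 2020: 5.0 years. There is no common day.

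**2. What can the planned estimates identify?** Let b be the log hazard ratio (HR) for SARI before the pandemic, d the disease difference, and t the period change in the association, taken to act on both diseases in 2020/21.

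- Planned: log HR (COVID-19, 2020/21) = b + d + t.
- Planned: log HR (SARI, 2015-2020) = b.
- Their difference is d + t. Two estimates serve three unknowns (rank 2 of 3).
- Add log HR (SARI, 2020/21) = b + t. The same-period difference is then d, and the SARI difference between periods is t (rank 3 of 3).

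**3. How large could the effect be?** On the ratio scale, observed ratio of HRs = disease ratio × period ratio. The period ratio is not in the documents; 0.8 to 1.25 is assumed.

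| Disease ratio | Period ratio | Observed ratio |
|---|---|---|
| 1.0 | 0.8 | 0.80 |
| 1.0 | 1.0 | 1.00 |
| 1.0 | 1.25 | 1.25 |
| 1.2 | 0.8 | 0.96 |
| 1.2 | 1.25 | 1.50 |

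The Study Size section gives one indication that the SARI setting changed: about 7,000 SARI intensive care admissions per year for cohort 4, against about 3,500 patients in all for cohort 5. At the earlier rate, 7,000 × 1.43 gives about 10,040, and 3,500/10,040 is about 35%, or about 2,440 per year. This is a change in absolute numbers. If exposed and unexposed rates fell alike, the HR would not move (0.35/0.35 = 1.0).

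**4. Would a same-period SARI analysis be informative?** This is illustrative, for the intensive care endpoint. It treats the Aim 2 counts as events and assumes an exposure prevalence p of 10% to 30%, which the protocol does not give. Variance of log HR = 1/(E × p × (1 − p)), and the variances of the two log HRs are summed.

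- Same period (11,000 COVID-19, 3,500 SARI), p = 0.1: SE = √(1/990 + 1/315) = 0.065. The 95% interval factor is exp(1.96 × 0.065) = about 1.14, and the ratio detectable with 80% power is exp(2.80 × 0.065) = about 1.20.
- Same period, p = 0.3: SE = √(1/2,310 + 1/735) = 0.042. The interval factor is about 1.09 and the detectable ratio about 1.13.
- Planned contrast (11,000 COVID-19, 5 × 7,000 = 35,000 SARI): detectable ratio about 1.11 at p = 0.1 and 1.07 at p = 0.3.

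The same-period contrast is less precise but still useful.

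**The case against.** The historical comparator is a declared choice with a reason: Study Size explains the five-year window by recency and numbers. Objective 3 does not ask for a concurrent comparison, and a pre-pandemic SARI cohort cannot contain undetected COVID-19. These points stand, and they argue for keeping cohort 2.

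The plan also compares hazard ratios within cohorts, so an equal period effect cancels. That stands too, and it limits the point to differential change. A reader might infer from the fall to about 35% that the SARI hazard ratio moved. The documents do not support that: the figure sets patients against admissions, comes from the Aim 2 intensive care cohorts rather than the Aim 1 endpoint, and is not split by exposure. The Bias text likewise concerns exposure to COVID-19 by condition. It makes equal effects unsafe to assume but does not show a shift in the SARI association.

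Some handling of time exists. All cohort 1 patients enter on one date, so the time-dependent terms there follow calendar time, but only within the pandemic. The 1-year cap is conditional and brings in no 2020/21 SARI data. The E-value addresses unmeasured confounding in general, and the condition-specific analyses repeat the same two-period comparison. Nothing under Sensitivity analyses compares the diseases within one period for Aim 1.

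Finally, a reader might think that cohort 1 already has a SARI outcome. It does not. The protocol links Hospital Episode Statistics (HES), which covers all NHS admissions, and the ICNARC Case Mix Programme; an outcome would have to be defined from these.

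**Conclusion.** The point holds in a limited form. For Objective 3, disease and period are fully aliased, and no listed analysis separates them, although the protocol recognised and addressed the same problem for Aim 2. A difference between the cohort 1 and cohort 2 hazard ratios cannot be attributed to disease on this plan.

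The size is unknown. The bias factor equals the period change in the exposure-outcome association, and the documents give no value for it; 0.8 to 1.25 is only an assumed range, and 1.0 is possible.

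A reader might go further and ask that the same-period contrast replace the planned one as the main answer. The documents do not settle that. It would exchange period confounding for fewer SARI events and some misclassified early COVID-19, which is a debatable trade. Adding it as a secondary analysis is a cheap improvement, not the repair of a fatal flaw.

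**What to change.** Add a pre-specified secondary analysis for Objective 3:

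- **Population and time:** the cohort 1 population, from 24 January 2020 to study end, with the same exposure and covariates.
- **Outcome:** SARI by the cohort 2 definitions (J09-J22 in HES; the listed RE codes in the Case Mix Programme). Exclude admissions with a COVID-19 code or with a positive test from 14 days before admission to discharge, which reuses the protocol's own testing window.
- **Severe COVID-19:** treat it as a censoring event in a cause-specific model, with a competing-risk check.
- **Like with like:** compare the separate hospital-admission and intensive care outcomes already listed as secondary in cohorts 1 and 2, or use a composite whose death component matches across the outcomes compared.
- **Reporting:** show the same-period COVID-19 v SARI contrast beside the cohort 1 v cohort 2 contrast. Attribute a difference to disease only if the same-period contrast supports it. Use cohort 2 to show whether the SARI association itself moved between periods.

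The cost is one extra outcome and model, with the exclusion and censoring rules above, on data already linked. The downsides are fewer SARI events than in five pre-pandemic years and some undetected COVID-19 among the early 2020 SARI events; both should be stated. If the analysis is not added, the protocol should say that the Objective 3 contrast cannot separate disease from period.
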